## **APPENDIX 2. BIOPSY SAMPLE COLLECTION**

A liver biopsy can be performed in two separate and non-exclusive occasions:

- 1- Prior to enrollment into the LTFU, subjects will be asked to provide a liver biopsy, at the discretion of the Principal Investigator and Sangamo Medical Monitor. This request is optional and does not preclude the patient from joining the LTFU study. The proposed mechanism of action of SB-FIX is to introduce the Factor IX transgene into a precise location in the albumin locus. To determine the level of insertion of the factor IX gene after SB-FIX injection, liver tissue will be obtained by liver biopsy, unless contraindicated by the Principal Investigator or physician, and analyzed by high-throughput sequencing of the albumin locus.
- 2- AFP levels will be monitored throughout the study, and abnormal results will be investigated by clinical evaluation and MRI. Any subject who has an elevated alpha fetoprotein and MRI mass suspicious for hepatocellular carcinoma (HCC) or greater than 2 cm will undergo biopsy using surgical doses of FIX replacement. Histopathologic examination and genomic analysis (e.g., sequencing of the albumin locus and integration site analysis) will be performed in an attempt to identify the origin and nature of the tumor.

### **Liver Biopsy Sample Collection and Tissue Preparation**

Liver biopsy will be obtained prior to enrollment into the LTFU at the discretion of the Principal Investigator and Sangamo Medical Monitor, and/or if a liver mass is detected during the study. A liver biopsy sample will be collected in 10% neutral buffered formalin and processed for histopathological evaluation by the site. A second liver biopsy sample will be flash frozen in liquid nitrogen. Samples may be stored in a -80°C freezer before shipment. Details of the histopathological evaluation, including the weight of liver tissue obtained from each biopsy sample, will be summarized in a report and sent to the sponsor.

The efficiency of SB-FIX in targeting insertion of Factor IX donor transgene to the liver will be measured by site specific molecular analysis of integration events at the albumin locus.

Additionally, the frequency of other genomic modification events like small insertions and deletions (indels) will be determined by Next Generation Sequencing (NGS) at the albumin locus and at the SMCHD1 locus, the only known off-target site of SB-FIX.

### APPENDIX 3. IMMUNOSUPPRESSION REGIMEN

Steroid prophylaxis will not be instituted at the initiation of this study. Subject's LFTs will be monitored twice a week and FIX activity will be monitored once a week for the first 12 weeks after SB-FIX infusion. The same monitoring schedule of LFTs and FIX activity will continue after Week 12 if the subject is receiving steroid treatment.

If a subject experiences an increase in ALT >2 times of the baseline value, oral prednisone at a dose of 60 mg/day will be instituted, followed by a rapid tapering targeted at 50% per week as provided in the table below.

	WK 1	WK 2	WK3	WK 4
Prednisone	60 mg/day	30 mg/day	15 mg/day	5 mg/day

Prednisone may be replaced by an equivalent product from the corticosteroids class, for example methylprednisolone or prednisolone, oral or intravenous, at the discretion (for type of corticosteroid and possible dose adjustment based on weight) of the investigator.

Tapering will only proceed when ALT value has stabilized (three consecutive values under the ULN with no increase of ALT) or FIX levels have stabilized or increased during the preceding week. If a subject's LFTs again increase, or FIX levels decrease > 10% while on prednisone, the dose of prednisone may be adjusted (increased) after consultation with the Medical Monitor.

A short course of steroid (prophylaxis or post-exposure at a defined time point after SB-FIX infusion) will be initiated for the remaining untreated subjects if ALT elevation >2 times of baseline is observed in two subjects, or ALT elevation > 5 times of baseline is observed in one subject. The SMC will be consulted in determining the timing of the initiation of the steroid treatment based on the timing of ALT increases or FIX decreases from the previously treated subjects.

An ACTH stimulation (cosyntropin) test will be performed at the end of the taper to ensure that the hypothalamic-pituitary-adrenal axis has not been suppressed.

If a subject develops transaminitis during or after the prophylactic course of prednisone treatment, Medical Monitor should be consulted to determine an appropriate course of treatment.

Twice weekly LFT's and weekly FIX activity measurements should continue until the subject's prednisone course has been terminated.

MedDRA	Medical Dictionary for Regulatory Activities
NAB	Neutralizing Antibody
NHEJ	Non-homologous End-joining
NHP	Non-human Primates
NIH	National Institutes of Health
PCR	Polymerase chain reaction
PI	Principal Investigator
RBC	Red Blood Cell
RNA	Ribonucleic Acid
SAE	Serious Adverse Event
SMC	Safety Monitoring Committee
SNP	Single Nucleotide Polymorphism
SOC	System Organ Class
WHO	World Health Organization
ZFN	Zinc Finger Nucleases

1. Introduction

Hemophilia B is an X-linked recessive bleeding disorder caused by mutations in the gene encoding blood coagulation Factor IX (FIX). FIX is a serine protease that is critical for the intrinsic clotting pathway. It occurs in about one in 25,000 males with a prevalence of approximately 4,000 in the United States (<http://www.hemophilia.org/About-Us/Fast-Facts>). The disease manifestation varies depending upon the level of Factor IX clotting activity.

In this study, it's proposed treating hemophilia B via a novel strategy which places a corrective FIX transgene into the genome at the albumin locus, under the control of the subject's own endogenous albumin locus, resulting in liver-specific synthesis of Factor IX. Successful preclinical studies with this albumin ZFN/targeted Factor IX strategy in FIX deficient mice have been published (Sharma 2015). Adeno Associated Virus (AAV) vectors encoding mouse-specific ZFNs targeting the albumin locus in the mouse genome and a human factor IX donor were injected into normal and hemophilia B mice. Measurement of hFIX in normal mice showed expression at >3000 ng/ml (>50% normal FIX levels) that was stable for over a year. There was a dose response, with circulating FIX increasing from 100 ng/ml to >10,000 ng /ml with a 2 log increase in AAV vector dose. Similarly, increases in FIX levels, with associated normalization of aPTT, were seen in Hemophilia B mice.

The purpose of the Statistical Analysis Plan (SAP) is to describe the analyses and data presentations for Sangamo's protocol SB-FIX-1501 (Amendment 8, 20March2020). This SAP outlines the types of analyses that will address the study objectives and explains in detail how the data will be handled and analyzed. It contains the definitions of analysis sets and statistical methods for the analysis of endpoints. Since this is an exploratory Phase I study, all analyses will be descriptive and exploratory in nature. No hypotheses testing will be carried out.

2. Objectives

2.1. Primary Objective

The primary objective of this study is to evaluate the safety and tolerability of SB-FIX.

2.2. Secondary Objectives

The secondary objectives of this study are to evaluate:

- Change from baseline in FIX antigen and activity levels
- Change from baseline in use of Factor IX replacement therapy
- Change from baseline in frequency and severity of bleeding episodes
- Immune response to FIX

- Presence and shedding of AAV2/6 vector DNA by PCR in plasma, saliva, urine, stool and semen

2.3. Exploratory Objectives

The exploratory endpoint will not be analyzed in data listing and table. It will be discussed in a separate document.

3. Investigational Plan

3.1. Overall Study Design and Plan

This is a Phase I, open-label, ascending dose study of male subjects, at least 12 years of age, with severe hemophilia B who are without inhibitors to FIX and have no hypersensitivity to recombinant FIX. The duration of study participation will be approximately 39 months for each subject, including 3 months for screening, 36 months for treatment and study follow-up. Accrual is planned for 20 months.

Up to 16 subjects will be enrolled. Among them, 13 subjects will be aged at 18 years or older and potentially three subjects will be between 12-17 year old. Two subjects ≥ 18 years old will be enrolled in each of two dose cohorts.

Subjects who satisfy all inclusion/exclusion criteria will be enrolled into one of the following two treatment cohorts:

Cohort 1: Total rAAV Dose (vg/kg) 1.00E+13

Cohort 2: Total rAAV Dose (vg/kg) 5.00E+13

A single dose of each of the 3 components of SB-FIX (ZFN1, ZFN2, and cDNA Donor) will be added to 200 mL diluent (refer to Study Pharmacy Manual) and adjusted to 0.25% human serum albumin, and then administered via intravenous infusion while the subject is in the hospital or acute care facility. Subjects will remain in the hospital or an acute care facility for 24 hours after the end of the SB-FIX infusion for observation, and will be discharged when all AEs, concomitant medications, and vital signs (temperature, pulse, respiratory rate, and blood pressure) are stable.

After being discharged from the hospital or acute care facility, the subjects will be evaluated at the study center every two weeks for the first 12 weeks, every four weeks between Months 3 and 12, and every 3 months during Year 2 and Year 3, or until enrollment into LTFU study. The liver function tests (Alanine Aminotransferase (ALT), Aspartate Aminotransferase (AST), bilirubin, alkaline phosphatase (ALP), LDH, total protein, and albumin) will be performed 2 times per week for evaluation of AAV mediated immunogenicity during the first 12 weeks after SB-FIX infusion, and then every 4 weeks between Months 3 to 12, and every 3 months in Year 2 and Year 3, or until enrollment into LTFU study.

3.2. Study Endpoints

3.2.1. Primary Endpoint

- Grading of adverse event (AE) and serious adverse event (SAE)
- Change from baseline in laboratory evaluations

3.2.2. Secondary Endpoints

- Changes in FIX antigen and FIX activity levels from baseline over time
- Change from baseline in the number of FIX units infused per week
- Change from baseline in number and severity of bleeding episodes
- Changes in neutralizing antibodies to FIX from baseline over time
- Presence and shedding of AAV2/6 vector DNA, by PCR in plasma, saliva, urine, stool and semen over time

3.3. Treatments

The final investigational products SB-FIX include three AAV2/6 components in separate vials:

- Left ZFN (SB-42906)
- Right ZFN (SB-43043)
- Human FIX Donor cDNA with human albumin homology arms (SB-F9)

3.4. Dose Modifications

No dose modifications are possible within an individual subject as this is a single infusion study.

4. General Statistical Considerations

Study day will be calculated as event/assessment date - date of SB-FIX infusion. Thus, the date of SB-FIX infusion is considered as Day 0. The relative study day for assessment will be derived as the assessment date subtracted from the date at Day 0.

Baseline is defined as the last non-missing assessment prior to the SB-FIX infusion. Measurements that are obtained after infusion will be considered as post-baseline values. Change from baseline is defined as post-baseline assessment minus baseline assessment.

Summary tables will be provided when there is more than one enrolled subject in a cohort. Otherwise, data will be presented in the form of a listing.

Continuous variables will be summarized using the following descriptive statistics: the number of subjects (n), mean, standard deviation (SD), median, minimum and maximum,

where appropriate. Categorical variables will be summarized using the frequency count (n) and percentage (%) of subjects for each category, where appropriate.

No imputation will be performed for missing data unless otherwise specified.

Data will be displayed in all listings sorted by treatment cohort and subject identifier.

All analyses will be conducted using SAS[®] Version 9.3 or higher. The Medical Dictionary for Regulatory Activities (MedDRA) version 23.0 will be used for coding adverse events. Prior or concomitant medication data will be coded using the World Health Organization (WHO) Drug Dictionary Global B3 March 2020.

4.1. Sample Size

This is a phase 1 study with up to 16 evaluable subjects. This study is exploratory and its sample size is not determined by statistical power considerations.

In order to have an evaluable sample size, subjects who prematurely discontinue the study prior to 12 months of the study follow-up (i.e., were enrolled but not dosed, or lost to follow-up) may be replaced with another subject.

4.2. Analysis Set

4.2.1. Enrolled Set

The enrolled set will include subjects who enrolled in this study.

4.2.2. Safety Set

The Safety set will include all subjects who enrolled in this study and receive any portion of the SB-FIX infusion.

Unless specified otherwise, all collected data used for table summaries will be based on Safety set, and corresponding listings will be provided for enrolled set. Any percentage will be calculated based on number of subjects for the Safety set if not otherwise specified.

5. Subject Disposition

5.1. Disposition

A disposition table of subjects will be presented, which will include the number and percentage of subjects for the following categories: subjects in Enrolled set and Safety set, subjects who completed the study, and subjects who early terminated from the study. The disposition will be summarized by treatment cohort. The percentages will be based on the number of subjects in each treatment cohort and overall. The reasons for early termination of the study will also be summarized in the table.

Subject disposition and analysis set assignment data will be presented in a listing.

5.2. Protocol Deviations

Protocol deviation data will be presented in the table and listing. All COVID-19-related protocol deviations will be summarized in the table and flagged in the listing.

6. Demographics and Baseline Characteristics

6.1. Demographics

The demographics will be summarized by treatment cohort and overall. The following variables will be included:

- Age (Years)
- Race (White, African American, Asian, American Indian or Alaska Native, Native Hawaiian or Other Pacific Islander, Other)
- Ethnicity (Hispanic or Latino, Not Hispanic or Latino)
- Weight and Height at baseline prior to dosing

Age will be derived as (Date of inform consent – date of birth + 1)/365.25.

The demographics data will be listed as well.

6.2. Medical History

The number and percentage of subjects with any medical history will be summarized by treatment cohort and for each body system code. Body system codes are recorded on the eCRF. Percentages will be calculated based on number of subjects for the Safety set.

Subject medical history data including specific details will be presented in a listing.

7. Treatments and Medications

7.1. Concomitant Medications

The concomitant medication is defined as any medication (including those given in treatment of AEs) taken by the subject from screening throughout the course of the study.

Concomitant medications will be coded using the WHO Drug Dictionary. The dictionary will be updated throughout the life of the project to allow for the most recent version of the dictionary to be used. The medication names will be coded according to the Anatomical Therapeutic Chemical (ATC) class level 4 and preferred terms provided in the dictionary.

Concomitant medications will be summarized by providing the number and percentage of subjects by ATC class and preferred term for each treatment cohort and overall. ATC classes will be sorted in decreasing order of frequency based on the total number of subjects who take each medication in the total column, while preferred terms within each drug class will be presented alphabetically. In addition, the total number of medications and the number and percentage of subjects receiving at least 1 concomitant medication will

also be presented. If a subject has multiple medications for a given preferred term the subject will only be counted once.

All concomitant medications will be presented in a listing.

7.2. Study Treatments

The prepared investigational product will be intravenously infused at 100 mL /hour using a constant rate infusion pump on Day 0 while the subjects are in the hospital or an acute care facility. As it's a single infusion study, compliance or modification data is not applicable.

All infusion data including specific details will be presented in a listing.

8. Endpoint Analysis

8.1. Primary Analysis

The primary analysis in this study aims to assess the safety and tolerability of SB-FIX infusion by the grading of adverse event, serious adverse event and change from baseline in laboratory evaluations.

8.1.1. Adverse events

A treatment-emergent adverse event (TEAE) is defined as any event which occurs on or after the date of infusion, or an event that occurs prior to start of infusion and has frequency, intensity, or the character of the condition that worsens after administration of study treatment.

To identify TEAE, if the AE end date is partial, it will be imputed as follows (where UK and UKN indicate unknown or missing day and month respectively):

Partial end dates

- UK-MMM-YYYY: Assume the last day of the month;
- DD-UKN-YYYY/UK-UKN-YYYY: Assume 31-DEC-YYYY.

If the AE end date is on or after infusion date (after any imputation) or completely missing, the AE onset date will be compared with infusion date. In the event that only a partial start date (month/year) is available, it will be handled as follows:

Partial onset dates

- UK-MMM-YYYY: If the month and year are different from the month and year of the infusion date, assume 01-MMM-YYYY. If the month and year are the same as the infusion month and year, and the end date (after any imputation) is on or after the infusion date, then assume the infusion date. If the month and year are the same as the infusion month, and year and the end date (after any imputation) is prior to the infusion date, then assume the end date for the onset date.

- DD-UKN-YYYY/UK-UKN-YYYY: If the year is different from the year of infusion, assume 01-JAN-YYYY of the collected year. If the year is the same as the infusion year, and the end date (after any imputation) is on or after the infusion date, then assume the infusion date. If the year is the same as the infusion year, and the end date (after any imputation) is prior to the infusion date, then assume the end date for the onset date.

If the AE end date is complete and the partial AE start date imputed by the rules above is after the AE end date, then the start date will be imputed by the AE end date.

All AEs will be coded according to the most recent version of the MedDRA. Severity will be categorized by toxicity grade according to the Common Terminology Criteria for Adverse Events (CTCAE) Version 4.03.

AEs not listed in the CTCAE version 4.03 will be evaluated by using the following criteria:

- Grade 1, Mild: Symptoms causing no or minimal interference with usual social & functional activities
- Grade 2, Moderate: Symptoms causing greater than minimal interference with usual social & functional activities
- Grade 3, Severe: Symptoms causing inability to perform usual social & functional Activities
- Grade 4, Potentially Life-threatening: Symptoms causing inability to perform basic self-care functions, OR medical or operative intervention indicated to prevent permanent impairment, persistent disability, or death
- Grade 5: For any AE where the outcome is death.

Relationship of Adverse Events to Study Drug

The relationship of AEs to study drug has two categories: Related and Not related. The relationship of the AE to the investigational drug will be determined by the principal investigator. Any AE that does not meet the definition of a suspected AE reaction will be categorized as Not Related. No imputation will be done for missing relationship.

Severity of Adverse Events

All AEs will be summarized by maximum severity (CTCAE Grade 1, 2, 3, 4 and 5). If a subject reports multiple occurrence of a specific event within a specific analysis period, the subject will be counted only once by the maximum severity. No imputation will be done for missing severity.

The incidence of AEs will be summarized in tables with count and percentage of subjects with AEs by system organ class (SOC) and preferred term. Unless otherwise specified, at each level of SOC or preferred term, a subject with multiple events will only be counted once per SOC or preferred term. Percentages of subjects with AEs will be calculated out of

the number of subjects in each summary cohort of the Safety set. Tables will be sorted by SOC in decreasing order on total frequency in overall group and preferred term in alphabet order.

The following categories of AE will be summarized:

- TEAEs
- Severity (CTCAE Grade 1, 2, 3, 4 and 5) of TEAEs
- Relationship of TEAEs to study treatment
- Grade 2 or greater TEAEs
- SAEs
- Grade 2 or greater SAEs
- AEs leading to death
- AEs leading to study discontinuation

All AEs will be presented in data listings. TEAEs and SAEs will be flagged in the listings.

8.1.2. Laboratory Evaluations

The laboratory assessments include serum chemistry and metabolic panel, liver panel, CBC w diff and Platelet, and urinalysis with microscopic exam. The lab assessments will be evaluated over time on the study except urinalysis. Urinalysis assessments will only be collected at screening. All summaries will be based on the SI units, and missing values will not be imputed. Summary statistics of the observed values and change from baseline will be provided at the scheduled visits for serum chemistry and metabolic panel, liver panel, and CBC w diff and Platelet parameters by treatment cohort. The number and percentage of subjects with shift on extreme post-baseline values in low/normal/high from baseline will be presented in a shift table for liver panel parameters. Extreme laboratory value is the lowest or highest category a patient has post-baseline for the laboratory parameter. If a patient has a value below the normal range and a value above the normal range, the value furthest from the normal range will be chosen.

The coagulation level (by PT, PTT, and INR) is assessed over time. The level of PT, PTT and INR will be summarized by treatment cohort and by visit for baseline, post-baseline and change from baseline values. Corresponding listing will be provided. The mean and standard error by cohort will be plotted for each coagulation parameter by timepoint and treatment cohort.

All laboratory data will also be presented in listings for each summary section with abnormal values flagged.

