#### **6.9 Months 15, 18, 21, 24, 27, 30, 33 and 36/End of Study (+/-1 months)**

Subjects will be evaluated every 3 months in Year 2 and Year 3 after SB-FIX infusion. The following assessments are performed at each visits Months 15, 18, 21, 24, 27, 30, 33 and 36/End of Study (+/-1 months) unless stated otherwise.

1. AE assessment
2. Assessment of concomitant medications
3. Physical exam
4. Weight
5. Vital signs
6. Abdominal exam for hepatomegaly
7. Neurologic cranial nerve exam and muscle strength testing of the upper extremities including shoulder, elbow and hands (Months 18, 24, 30, and 36)
8. Urinalysis with microscopic exam (Month 36 only)
9. Chemistry, liver, and metabolic panel
10. CBC with differential and platelet count

11. Coagulation screen (PT, INR, and PTT)
12. FIX antigen and activity levels
13. FIX inhibitor level
14. Assessment of bleeding episodes and FIX concentrates usage
15. Liver MRI or equivalent imaging technology (Months 18, 24, 30, and 36)
16. Circulating alpha fetoprotein level (Months 18, 24, 30, and 36)
17. ACTH stimulation test (only performed if at the end of prednisone [or equivalent] taper)

An End of Study (EOS) visit will be conducted prior to subject's enrollment into the LTFU study.

At the EOS visit, subjects will be invited to participate in the LTFU Study. Study subjects may participate in the LTFU Study after 12 months of follow-up in the SB-FIX-1501 study, in which case an EOS visit may be conducted any time after Week 52 in combination with or before the next scheduled study visit.. Informed consent will be obtained prior to participating in the LTFU Study.

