### **6.10 Early Termination Visit (ETV)**

Subjects who discontinue from the study prematurely or are withdrawn from the study will be asked to return to the study site for an Early Termination Visit (ETV). It is at the discretion of the Investigator to waive any procedures if it has been performed within the standard interval of scheduled study visits per protocol.

The following assessments and procedures will be performed at the ETV:

1. AE assessment
2. Assessment of concomitant medications
3. Physical exam
4. Weight
5. Vital signs
6. Abdominal exam for hepatomegaly
7. Neurologic cranial nerve exam and muscle strength testing of the upper extremities including shoulder, elbow and hands
8. Urinalysis with microscopic exam
9. Chemistry, liver, and metabolic panel
10. CBC with differential and platelet count
11. Coagulation screen (PT, INR, and PTT)
12. FIX antigen and activity levels
13. FIX inhibitor level
14. Assessment of bleeding episodes and FIX concentrates usage
15. ACTH stimulation test (only performed if at the end of prednisone [or equivalent] taper)
16. Liver MRI or equivalent imaging technology (if not performed within 6 months prior to the ETV)
17. Circulating alpha fetoprotein level
18. Vector genome in plasma, saliva, urine, stool, and semen by PCR

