Abdominal Exam for hepatomegaly		X				X	X	X	X
Vital signs	X	X	X	X	X	X	X	X	X
Neurologic cranial nerve exam and muscle strength testing of the upper extremities		X				X (WK 12 only)	X (Wks 24 and 52)	X (Months 18, 24, 30, and 36)	X
12-lead ECG	X								
Chest X-ray	X								
Urinalysis with microscopic exam	X							X (Month 36 only)	X
CBC w differential and platelet count	X	X	X	X		X (WKS 4, 8, 12)	X (WK 28,52)	X	X
Serum Chemistry, Metabolic Panel	X	X	X	X		X	X	X	X

APPENDIX 1. SCHEDULE OF EVENTS									
Procedure	Screening	Baseline (w/in 21 days before SB- FIX infusion)	Hospitalization or Acute Care Facility		Day 7 (+/-1 day)	Weeks 2, 4, 6, 8, 10, 12 (+/- 3 day)	Weeks 16, 20, 24, 28, 32, 36, 40, 44, 48, 52 (+/- 1 wk)	Months 15, 18, 21,24, 27, 30, 33, 36/EOS* (+/- 1 M)	Early Termination Visit
			Day 0	Day 1					
Liver Panel (b)	XX	X	X	X	X (2 x/wk)	X (2x /wk)	X (2 x/wk if using steroid)	X	X
Direct bilirubin	X								
Neutralizing antibodies to AAV 2/6	X								
Total antibodies to AAV2/6 (exploratory)		X				X (WKS 4, 8, 12)	X (WKS 24, 36, 52)		
Coagulation screen (PT, INR, and PTT)	X	X	X			X (WKS 4, 8, 12)	X	X	X
FIX activity	X	X		X	X	X (weekly)	X (Weekly if using steroid)	X	X
FIX antigen	X	X		X	X	X (WKS 4, 8, 12)	X	X	X
FIX inhibitor level	X	X		X		X (WKS 4, 8, 12)	X	X	X
HBV DNA, HBsAg, HCV RNA viral load, and HIV RNA viral load and HIV-1/2 antibody assay	X								
SNP assay	X								
Concomitant medication review (c)	X	X	X	X	X	X	X	X	X

APPENDIX 1. SCHEDULE OF EVENTS									
Procedure	Screening	Baseline (w/in 21 days before SB- FIX infusion)	Hospitalization or Acute Care Facility		Day 7 (+/-1 day)	Weeks 2, 4, 6, 8, 10, 12  (+/- 3 day)	Weeks 16, 20, 24, 28, 32, 36, 40, 44, 48, 52  (+/- 1 wk)	Months 15, 18, 21,24, 27, 30, 33, 36/EOS*  (+/- 1 M)	Early Termination Visit
			Day 0	Day 1					
AE assessment (c)		X	X	X	X	X	X	X	X
ZFN immunogenicity (exploratory)		X				X (Wks 4, 8, 12)	X (Wk 24, 36, 52)		
Assessment of bleeding episodes and FIX concentrates usage		X	X	X	X	X	X	X	X
ACTH stimulation test (d)		X				X	X	X	X
Prednisone administration (or equivalent) if indicated		X	X	X	X	X	X		
SB-FIX infusion			X						
Vector genome in plasma, saliva, urine, stool and semen by PCR (e)		X		X	X	X (Wks 2, 4, 8, 12)	X		X
FIX genome sequencing (f)	X								
Liver MRI (g)	X					X (WK 12 only)	X (Wks 24 and 52)	X (Mos 18, 24, 30, and 36)	X

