8.2.5. Vital Signs

The vital sign data collected after infusion until 2 hours post-infusion will be pooled for each subject and the mean of pooled data will be summarized by cohort as one timepoint,

ie 2 hour post-infusion timepoint. The data collected at Baseline, and post-infusion will be summarized by timepoint for each cohort. Change from baseline will be summarized too. The vital sign data will be listed.

9. Other Analysis

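### The SAP says urinalysis is collected only at screening, but the protocol repeats it at Month 36 and early termination; the 2-hour vital-sign mean and the liver shift table could also be improved cheaply

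*SAP*

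**What the plan says.** **Urinalysis.** SAP 8.1.2 includes urinalysis with microscopy in its list of laboratory assessments, but then says "The lab assessments will be evaluated over time on the study except urinalysis" and "Urinalysis assessments will only be collected at screening". The protocol has it at screening (6.1), again in 6.9 as "Urinalysis with microscopic exam (Month 36 only", and as item 8 of the early termination list in 6.10 ("Urinalysis with microscopic exam"). The urinalysis row of the Schedule of Events (Appendix 1) marks the same three occasions. SAP 3.2.1 gives as part of the primary endpoint "Change from baseline in laboratory evaluations". SAP section 4 sets the reference value: "Baseline is defined as the last non-missing assessment prior to the SB-FIX infusion".

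**Vital signs.** SAP 8.2.5 says "The vital sign data collected after infusion until 2 hours post-infusion will be pooled for each subject", and the subject mean becomes a single timepoint. Later readings are summarised by timepoint. Protocol 6.4 has readings every 15 minutes until stable, then every 30 minutes to 2 hours post-infusion, around an infusion of 2 to 8 hours.

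**Liver shift table.** SAP 8.1.2 assigns each subject one extreme post-baseline category (low, normal or high) per liver parameter. A subject with both low and high values is classified by whichever lies further outside the range.

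**The concern.** The urinalysis sentence is a factual error in the section that defines the primary laboratory analysis. A programmer who follows it will build no post-baseline urinalysis table and may not expect any later records.

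The other two points concern how well the tables show what the study is watching for. Protocol 7.1.3 names anaphylaxis and severe hypotensive crisis as possible infusion reactions, and averaging a window weakens a brief change. Protocol 11.2 lists transaminitis and reduced albumin synthesis among its key anticipated risks. The ALT thresholds in Appendix 3 are multiples of baseline, whereas the shift table is scaled only to the normal range.

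**Working it through.** The plan gives no figure to reproduce here: the sample size has no power basis and no test is planned. The check is a comparison of texts plus simple arithmetic.

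**1. Urinalysis**

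| Occasion | Protocol 6.1, 6.9, 6.10 | Appendix 1 | SAP 8.1.2 |
|---|---|---|---|
| Screening | yes | yes | yes |
| Month 36 | yes | yes | no |
| Early termination | yes | yes | no |

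The protocol agrees with itself and the SAP differs. The screening result is normally the last value before infusion, so it serves as baseline under SAP section 4 and a change can be described.

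- Upper limit: 1 post-infusion sample (Month 36 or early termination) × 16 subjects = 16, if no subject is replaced.
- Lower limit: 0. Subjects may move to the long-term follow-up study after 12 months (6.9), so they may have no Month 36 sample. The investigator may also waive early-termination procedures that were done recently (6.10).
- Planned summaries in the SAP: 0.

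**2. Vital signs**

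If one reading among *k* departs by *d* and the others do not, the mean moves by *d/k*. A fall of *d* = 30 mmHg is assumed for illustration.

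| Window opens at | Spacing | Readings *k* | Shift in mean (mmHg) |
|---|---|---|---|
| End of infusion | 30 min | 120/30 = 4 | 30/4 = 7.5 |
| End, plus a time-0 reading | 30 min | 5 | 30/5 = 6.0 |
| End of infusion | 15 min | 120/15 = 8 | 30/8 = 3.75 |
| Start, 2 h infusion | 30 min | (2+2)×60/30 = 8 | 30/8 = 3.75 |
| Start, 8 h infusion | 30 min | (8+2)×60/30 = 20 | 30/20 = 1.5 |

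The start-of-infusion rows are included because the window is not defined. SAP section 4 uses the same words, after infusion, for every post-baseline value, so the phrase in 8.2.5 does not settle whether readings taken during the infusion are pooled.

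**3. Liver shift table** (subject values assumed)

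- ALT from 1.5 to 2.9 × ULN: 2.9/1.5 = 1.93-fold, shown as high to high. Such a baseline is possible because exclusion criterion 12 applies only above 2.0 × ULN.
- ALT from 0.4 to 0.9 × ULN: 0.9/0.4 = 2.25-fold, above the 2 × baseline threshold of Appendix 3, shown as normal to normal.
- Albumin, using the general 35 to 45 g/L range in Protocol 1.8 (the laboratory's range may differ): a low of 33 g/L lies 35 − 33 = 2 below the range. It drops out of the table only if the same subject also exceeds 45 + 2 = 47 g/L.

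The by-visit tables do not fully fill the gap. Twice-weekly liver panels for 12 weeks give about 2 × 12 = 24 draws, against eight named visits from Day 1 to Week 12 (Day 1, Day 7, Weeks 2, 4, 6, 8, 10, 12). The SAP does not say how draws between visits enter tables built on scheduled visits.

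**The case against.** The case for treating this lightly is substantial.

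- **Listings.** SAP 8.1.2 promises listings of all laboratory data with abnormal values flagged, so late urinalysis results for at most 16 subjects would probably be seen. This largely stands. The promise is tied to each summary section, however, and urinalysis has no summary.
- **Small scale.** It is one panel, with at most one late result per subject, in a study without hypothesis tests. This stands and limits the weight of the point. It does not make the sentence true.
- **Version.** The SAP is written for Amendment 8 of 20 March 2020. The protocol copy reviewed has no title page, so the match could not be confirmed.
- **Vital signs.** The ordinary reading of the window is after the infusion ends, vital signs are outside the SAP's primary endpoint, and all readings are listed. The single-reading dilution would not apply if a fall persisted over several readings. These are fair limits. Closer spacing would dilute one aberrant reading further, and the window still needs a definition.
- **Liver.** Protocol 12.5.3 permits normal-range shift tables, so there is no contradiction. ALT above 2 × baseline leads to prednisone, so it should normally reach the adverse-event tables (Protocol 9.1.1, SAP 8.1.1) and the concomitant-medication table (SAP 7.1). Grade 3 or 4 worsening is reported as an adverse event unless covered by a diagnosis already reported (Protocol 9.3). By-visit tables give the minimum and maximum. The albumin example needs an unlikely pattern in one subject. All of this stands and is why the point is only an improvement.

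**Conclusion.** The point holds. SAP 8.1.2 misstates when urinalysis is collected and, followed as written, leaves the only scheduled post-infusion urinalyses out of the primary-endpoint summaries. The size is 0 to 16 results, depending on roll-over to long-term follow-up and on waivers. This should be corrected; it affects no inference, error rate or sample size.

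The vital-sign and liver points are matters of presentation, and no data are hidden. What remains untabulated per subject is narrow: mainly a Grade 1 or 2 ALT rise of no more than 2 × baseline, or one in a subject already on steroids, that the investigator does not judge clinically significant; and a brief vital-sign change not reported as an adverse event. The mmHg, ALT and albumin values are illustrations and not expected findings.

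**What to change.** - **SAP 8.1.2, urinalysis:** reconcile the sentence with Protocol 6.9, 6.10 and Appendix 1. Summarise Month 36 and early-termination results against screening, and give the number of subjects with a sample.
- **SAP 8.2.5:** state whether the pooled window opens at the start or the end of the infusion. Report each subject's minimum, maximum and largest change from the pre-infusion value, during the infusion and through 2 hours after it.
- **SAP 8.1.2, liver panel:** show low and high shifts separately. Add one table of worst post-infusion ALT and AST by multiple of baseline (up to 2×, above 2× to 5×, above 5×) and by CTCAE v4.03 grade, using all draws.

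The cost is SAP wording and a small amount of programming on data already scheduled, with no new visits or samples. The tables gain a few rows. The worst of many values runs higher than a typical value, so the new table must be labelled as worst post-infusion.
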